Topical negative pressure (TNP) is a frequently used method to promote the healing of surgical and non-surgical wounds (1). It uses suction to drain excess fluid from the wound thereby reducing the risk of seroma formation and the risk of infection by decreasing the bacterial load. It has also been shown to stimulate localized blood flow and tissue growth, partially by removing excess fluid but also via mechanical stimulation of nearby tissue (1, 3). Understanding these methods of action, TNP is used frequently in the health care setting to assist with wound healing. Management with TNP of chronic wounds and wounds at high risk for separation has been evaluated in many studies. For example, current studies have investigated the use of prophylactic TNP on closed surgical incisions, including investigations in traumatic injuries, hip arthroplasty, acetabular fractures, sternotomy wounds, vulvectomy incisions and post hysterectomy in obese women- all with promising results. However there is a relative lack of adequately powered patient-oriented evidence demonstrating TNP as a statistically significant agent for preventing or treating wound healing complications (1).

Presently, only one study has evaluated TNP in the obstetric population, specifically obese women undergoing a cesarean section. A retrospective cohort study was done at the University of Maryland to evaluate the efficacy of TNP in decreasing postoperative wound complications when placed over a clean, closed incision following cesarean section in obese patients. Their study demonstrated that there were no wound complications in the population receiving TNP versus a 10.4% complication rate in the control group receiving the standard postoperative dressing (2). However, their study was underpowered from its small sample size and did not show statistical significance.

Obesity is widely prevalent in the United States. In 2012, the CDC reported that 35.8% of women were obese, this prevalence increases as income decreases and is highest for non-Hispanic black women (2). Cesarean sections are considered clean-contaminated procedures; this alone increases the risk of a post-operative wound infection. Wound complications occur in 2.5-16% of cesarean deliveries, influenced by many different factors (5). Obesity is a risk factor that nearly doubles the rate of cesarean section; and the risk of post-operative wound infections in obese women after a cesarean

FORM: Application for Human Research

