NUMBER	FORM DATE	PAGE
F200	02/2014	6 of 14

section has been shown to double for every 5 unit increase in BMI above 30 kg/m². Given the prevalence and increasing rate of obesity, and the associated complications particularly with operative procedures, it is important that we re-evaluate how to manage the associated complications and utilize the best possible techniques to decrease maternal morbidity.

Additional co-morbidities increase the risk of wound complications in the setting of cesarean section. These morbidities include maternal diabetes mellitus, history of wound infection or breakdown, chorioamnionitis at the time of cesarean, HIV/AIDS, anticoagulant therapies and autoimmune conditions. These patients may also benefit from innovations in wound management.

This study aims to evaluate the use of TNP over a clean, closed incision following cesarean section in high risk women for preventing complications of wound healing. We hypothesize that using TNP over a clean, closed incision following cesarean section in high risk women will significantly decrease and possibly prevent complications to wound healing. This study will be powered appropriately in order to obtain statistically significant results. We anticipate that by using TNP immediately following the operation we can prevent seroma formation, decrease the bacteria load in the wound and stimulate wound healing all to the effect of minimizing or preventing wound separation/breakdown/necrosis.

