The postoperative care delivered to patients is on the 7th floor of the hospital, directly below the Labor and Delivery Unit. The same resident physicians and physicians staff this area.

5) Study Population

Pregnant women with high risk obstetric complications who present to Labor and Delivery at B-UMCT for care at time of delivery and/or to the clinic for a regularly scheduled visit will be potential individuals enrolled in our study.

Sample size calculations predict that with a wound breakdown rate of 20% in high risk patients, approximately 80 patients in each group would be needed to show a complication rate decrease to 5%. We will recruit a total of 200 patients, 100 in the control group and 100 in the study group.

When the women partake in the study device, they will no longer be pregnant as the device will be applied post operatively (after the cesarean section).

FORM: Application for Human Research		
NUMBER	FORM DATE	PAGE
F200	02/2014	8 of 14

6) Recruitment Methods and Consenting Process

Patients will be identified by the investigators during the course of their clinical work or by designated study personnel during pre-screening (see Appendix F). Patients eligible for inclusion in this study will be approached by the Principal investigator, Co-investigator, Senior Investigator, and/or study personnel if they meet the following criteria:

Inclusion criteria:

- 1) Maternal Age 18 or above
- 2) Cesarean delivery
- 3) Maternal condition which increases the risk of wound complication. These conditions include: Obesity (BMI >30), diabetes, HIV/AIDS, chorioamnionitis, rheumatologic disease, history of wound complication, anticoagulant therapy.
- 4) Patient able to read and speak English or Spanish (once the consent form has been approved, a translated Spanish consent will be submitted to the IRB for approval, no Spanish speaking patients will be recruited until approval is received)

Exclusion criteria:

- 1) Minors (<18 years of age)
- 2) Non-cesarean wound (ie tubal ligation wound)
- 3) No high risk maternal condition
- 4) Patient unable to read and speak English or Spanish.
- 5) Prisoners

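### Is the sample size of 200 undermined because the assumed 20% control rate is above the rates the protocol quotes?

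*Protocol*

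**What the plan says.** Protocol, Section 3, item 5) Study Population, states the planning condition: "with a wound breakdown rate of 20% in high risk patients, approximately 80 patients in each group would be needed". The target follows as "to show a complication rate decrease to 5" per cent. The total is then fixed: "We will recruit a total of 200 patients, 100 in the control group and 100 in the study group". No significance level, power or allowance for loss is given as a number, and no source is cited for the 20%.

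Item 1) Background supplies the rates against which the 20% can be compared. It describes a single earlier study of the treatment in obstetrics: "Presently, only one study has evaluated TNP in the obstetric population, specifically obese women undergoing a cesarean section". That retrospective cohort found "no wound complications in the population receiving TNP versus a 10.4% complication rate in the control group". The reference title describes the population as morbidly obese. For cesareans in general the background gives a range of 2.5-16%. It also says that the risk of wound infection in obese women was shown to "double for every 5 unit increase in BMI above 30".

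Item 6) sets eligibility. A woman qualifies with any one of several conditions: "These conditions include: Obesity (BMI >30), diabetes, HIV/AIDS, chorioamnionitis", and also rheumatologic disease, a previous wound complication or anticoagulant therapy. BMI has no upper limit.

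**The concern.** The 20% is about twice the only control rate the protocol gives for a high-risk group, and it exceeds the top of the general range. Item 5 also calls the starting rate wound breakdown and the target a complication rate. If breakdown is the narrower outcome, a like-for-like comparison would put the 20% further from the evidence. The earlier cohort is described as morbidly obese, while this trial enrols from BMI above 30. With the stated BMI gradient, one might infer a control rate below even 10.4%.

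What is at stake is power. The background criticises the earlier study as underpowered and promises that this one will be adequately powered. If the true control rate is near 10%, 200 women could miss a large relative benefit, and a null result might be read as evidence against the device.

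**Working it through.** **Inputs.** Control 20%, treated 5%, about 80 needed and 100 recruited per arm (item 5); 1:1 allocation (item 7); comparison rates 10.4%, 0% and 2.5-16% (item 1). A two-sided 5% level and 80% power are assumed, since the protocol states neither.

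**1. Reproducing the plan's figure.** The pooled normal formula is n = [1.960·√(2p̄(1−p̄)) + 0.842·√(p₁(1−p₁) + p₂(1−p₂))]² / (p₁−p₂)². With p₁ = 0.20, p₂ = 0.05 and p̄ = 0.125, the two terms are 0.917 and 0.383, so n = 1.300² / 0.0225 ≈ 75.1, or 76 per arm. With continuity correction it is 88. Exact Fisher power at 80 per arm is 79.3%. The plan's figure of about 80 is sound. Recruiting 100 leaves room for 20% loss (80/100).

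**2. Power at 100 per arm under other rates.** Full binomial enumeration, Fisher to uncorrected chi-square:

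| Control vs treated | Basis | Power |
|---|---|---|
| 20% vs 5% | the plan | 88-92% |
| 16% vs 4% | top general rate, 75% reduction | 77-85% |
| 10.4% vs 2.6% | earlier study's control rate, 75% reduction | 53-63% |
| 10.4% vs 5% | earlier study's control rate, the plan's target | 22-30% |
| 10.4% vs 0% | both rates of the earlier study | 95-99% |

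For 10.4% vs 2.6%, 80% power needs 156 per arm (181 with continuity correction). The low figures arise from joining one study's control rate to another source's effect. With both of that study's rates, 200 women are enough.

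**3. How firm is 10.4%?** Its denominator is not in the protocol. As an assumption, some fractions that round to 10.4%, with exact 95% intervals, are 5/48 (3.5-22.7%), 7/67 (4.3-20.3%), 8/77 (4.6-19.4%) and 13/125 (5.7-17.1%). For a study the protocol itself calls small, the interval may or may not include 20%.

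**4. Does the BMI gradient imply less than 20%?** Take rate = base × 2^((BMI−30)/5), which stretches an infection gradient to all complications. Starting from the general range at BMI 30, 20% is reached at BMI 45.0 (base 2.5%), 40 (5%), 35 (10%) or 31.6 (16%). The gradient can support 20% or undercut it, depending on the anchor. Reading it downwards from 10.4% requires the earlier cohort's BMI, which the protocol does not give, and ignores the other six entry conditions, which have no stated rates.

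**5. What would a sample size review do?** Consider a blinded pooled count after 100 women (50 per arm), extending to 180 per arm if there are 8 or fewer events. At 10.4% vs 2.6%, power rises to 79-85%, extension occurs 80% of the time and the expected total is 200 + 160 × 0.80 = 328. At 20% vs 5%, extension occurs 10% of the time (expected total 216). At 10.4% vs 0%, it extends 93% of the time (expected total 349), although 200 women already give 95-99% power. A pooled count cannot tell a low control rate from a very effective device.

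**The case for a change.** The strongest case for a change is that item 5 itself fixes the rates and the total, so a later analysis plan would not cure a poor choice. The 20% is above every rate quoted. If obese controls really have a 10.4% rate and make up 50-80% of the control arm (an assumption), the remaining controls must average (20 − 10.4f)/(1 − f), which is 30% at f = 0.5 and 58% at f = 0.8, for the arm to reach 20%. A source and a single outcome term would cost nothing, and the blinded check would protect power at little expense if the plan's rates are right.

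Part of this stands. The 20% is unsourced in this form, the wording moves between two terms, and power would be poor if the control rate were near 10% and the device did no better than a 75% reduction. The rest is weaker. The mixture calculation treats an imprecise retrospective figure as exact. This trial reassesses wounds and asks about complications prospectively at 2 and 6 weeks, so its rate need not match. The switch between breakdown and complication reads as loose wording for one outcome falling from 20% to 5%; it does not show that the 20% leaves out other complications. Section 4 lists a separate research protocol among the attachments, which is not shown and may carry the source.

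**Conclusion.** No change to the plan is called for. The sample size is correct for the rates on which it is expressly conditioned, and the trial misses no power that it states. The 20% is an optimistic-looking planning assumption that the documents neither support nor disprove. Across the scenarios checked, power at 100 per arm runs from 22-30% (10.4% vs 5%) to 95-99% (10.4% vs 0%), so the answer turns on rates the protocol cannot settle.

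Naming a source, labelling the figure an assumption or using one outcome term would be tidier reporting but would leave the design and the analysis as they are. Enrolling more is a resource trade-off for a single-site study planned for two years: up to 160 further women, often recruited needlessly if the device works as well as in the earlier cohort. If the event rate proves low, the confidence interval for the difference should guide how a null result is read. These conclusions rest on an assumed two-sided 5% test, 80% power for the sample sizes, and 100 evaluable women per arm.

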
2) Lay Summary (approximately 400 words)

We aim to carry out a randomized controlled trial. Patients with a condition that increases their risk of a wound complication will be approached for inclusion in the trial. Each participant agreeing to study inclusion will be randomized to either suture alone or to closure of their skin incision with suture and then with prophylactic placement of a wound vac (PICO). The wound vac will be left in place until the day of discharge. Prior to discharge, the bandage will be removed, the wound inspected and a new bandage will be reapplied to the wound. The patient will remove the bandage and wound vacuum on POD#7 at home. Both items can be discarded in a normal trash receptacle. We will also obtain

FORM: Application for Human Research

NUMBER	FORM DATE	PAGE
F200	02/2014	7 of 14

permission to call the participants for a patient satisfaction questionnaire at 1 week post-op, and possibly 2 and 6 weeks if they have not presented for their post op/partum appointments or the questionnaire could not be obtained at their visit. The wound will be re-assessed at their 2 week and 6 week post-op follow up visits. The patients will be assessed by either the Principal Investigator, Co-investigator and/or Senior Investigator at their post-operative clinic visits. The investigator will ask the patient if they have had any postoperative complications since their surgery and will be asked to detail any complications if they answer yes to this question. They will also be asked to confirm that their wound has completely closed at this time.

3) Setting of the Human Research

Patients being approached for inclusion in this study are those presenting to labor and delivery for delivery care or to B-UMCT for their regularly scheduled clinic visit ([name]).

4) Resources available to conduct the Human Research

The Labor and Delivery unit at the Banner –University Medical Center comprises a triage area, up to 14 laboring rooms and 2 fully operational operating rooms.

There are 16 resident physicians, 2 clinical fellows and multiple OBGYN physicians available for the medical care of pregnant and laboring women. There is also around the clock nursing and anesthesia care available 7 days per week.

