There is a small risk of loss of protected health information. The PI will mitigate this risk by keeping all consents in a locked cabinet and not keeping any patient identifiers with the data analysis documents.

9) Potential benefits to subjects and/or society

Patients will receive no monetary benefit from being in this study.

If the hypothesis of this study is correct, those in the treatment arm (ie the wound vac arm) may experience a lower rate of wound complications.

Wound management is a common clinical problem encountered in obstetrics. Implications of a lower complication rate with the utilization of wound vacs would include offering this treatment in high risk groups in the future.

10) Provisions to protect the privacy of subjects and the confidentiality of data

Privacy of subjects will be respected at all times during the study. Patients will only be consented in a private area (pre-operative area, clinic room or laboring room). Patients are asked during all encounters with a physician whether or not they would like their family or friends present. Patients will not be required to have support people leave the room for inclusion in the study.

Patient confidentiality will be respected at all times. The records review required for the study will only be performed by those personnel appearing on the VOTF. All documents with traceable patient data (ie consent forms/data collection forms) will be stored in a locked cabinet in the fellow’s office (Room 8327 G). These records will be stored for a period of 6 years.

A data sheet will be created to include all data pertaining to the study without any patient identifiers. This document will be kept separate from the consent forms and data collection forms.

Additionally, a REDCap database will be used to facilitate tracking patient follow-up and statistical analysis when study procedures are completed. The REDCap database will store identifiable information. The REDCap data base will be maintained for 6 years after completion of the study.

11) Access to Private Information

a. Authorization for Access to Protected Health Information

FORM: Application for Human Research

NUMBER	FORM DATE	PAGE
F200	02/2014	11 of 14

Patients agreeing to participate in this study will be made aware that record review of their protected health information will occur as a part of the study. The consent form includes a HIPPA consent.

b. Authorization for Access to Educational Information

N/A

12) Cost to subjects

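### Does the mix of wound breakdown and complication in the sample-size sentence, with no named primary endpoint or deciding visit, call for a change?

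*Protocol*

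**What the plan says.** All references are to Section 3 of the Protocol.

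- **Sample size (item 5, Study Population).** The control rate is a "wound breakdown rate of 20% in high risk patients, approximately 80 patients in each group would be needed to show a complication rate decrease", and the target is given in the words "needed to show a complication rate decrease to 5" percent. The plan then recruits 100 per group. Significance level, sidedness and power are not stated.
- **Background rates (item 1).** "Wound complications occur in 2.5-16% of cesarean deliveries, influenced by many different factors". For obese women, the one earlier obstetric study is reported as having no complications with the device "versus a 10.4% complication rate in the control group receiving the standard postoperative dressing".
- **Hypothesis (item 1).** The device "will significantly decrease and possibly prevent complications to wound healing".
- **Risk factors (item 1).** The list includes "history of wound infection or breakdown".
- **Benefit (item 9).** Women in the device arm "may experience a lower rate of wound complications".
- **Follow-up (item 2, Lay Summary).** "The wound will be re-assessed at their 2 week and 6 week post-op follow up visits". Women are asked whether any complication has occurred after the operation, and whether the wound is fully closed.

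The attachment list (Section 4) names a separate research protocol and a data collection form. Neither is at hand.

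**The concern.** A sample-size calculation should describe the event that will be analysed. Here the starting rate is labelled breakdown and the target rate complication. The risk-factor list names infection and breakdown as two things, so the terms need not be identical. The aim, hypothesis and benefit statement lean towards complications in general, while the 20% is attached to breakdown.

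Two consequences would follow if this were more than loose wording. First, power could be lower than it appears: the rates the Protocol quotes for complications (10.4% in obese controls, 2.5% to 16% across cesareans) are all below 20%. Second, with two outcome terms and two visits open, the most favourable combination could be chosen after the results are seen, which would raise the false-positive rate.

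**Working it through.** **Inputs.** Rates of 20% and 5%, about 80 per group needed and 100 per group planned (item 5); 1:1 allocation (item 7); 10.4% against 0% in the earlier study (item 1). Assumed, because not stated: two-sided 5% and a target power of 80%.

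**1. Does the stated figure reproduce when both rates refer to one event?** With p the mean of the two rates,

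n per arm = [1.96·√(2p(1−p)) + 0.8416·√(p1(1−p1) + p2(1−p2))]² / (p1−p2)²

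For p1 = 0.20 and p2 = 0.05, p = 0.125. The two roots are √0.21875 = 0.4677 and √0.2075 = 0.4555.

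n = (1.96 × 0.4677 + 0.8416 × 0.4555)² / 0.15² = (0.9167 + 0.3834)² / 0.0225 = 75.1, so 76 per arm.

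The continuity-corrected figure is 88. Fisher's exact test passes 80% power at 82 per arm. The Protocol's approximate 80 lies within this range.

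**2. Power at the planned size.** Power = Φ{[(p1−p2)·√n − 1.96·√(2p(1−p))] / √(p1(1−p1) + p2(1−p2))}

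- 80 per arm: (0.15 × 8.944 − 0.9167) / 0.4555 = 0.93, power 82.5% (Fisher 79.3%).
- 100 per arm: (0.15 × 10 − 0.9167) / 0.4555 = 1.28, power 90.0% (Fisher 88.3%).

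**3. Do the lower complication rates follow from the naming?** The same formula at 100 per arm gives:

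| Control to device | Power | Source of the pair |
|---|---|---|
| 10.4% to 5% | 30% | control rate from one study, device rate from item 5 |
| 16% to 5% | 72% | top of the all-cesarean range, device rate from item 5 |
| 10.4% to 2.6% | 61% | 75% relative reduction kept |
| 16% to 4% | 81% | 75% relative reduction kept |
| 10.4% to 0% | 92% | the earlier study's own pair |

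The first four pairs appear nowhere in the Protocol. They also conflict with the premise of the concern. If the two terms differ, breakdown is one kind of complication, so

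P(any complication) ≥ P(breakdown) = 20%.

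The broader endpoint cannot then have a control rate of 10.4% or 16%. A broader endpoint with assumed control rates above 20% gives, at 100 per arm:

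- 75% relative reduction kept: 96% (25% to 6.25%) and 99% (30% to 7.5%).
- 15-point difference kept, so a weaker relative effect: 80% (25% to 10%) and 72% (30% to 15%).

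The naming therefore does not establish the direction of any change in power.

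**4. One event or two?** Item 5 speaks of a decrease from one rate to another, which makes sense only for a single event. Where the background lists earlier infection or breakdown as a risk factor, the eligibility criteria in item 6 give the corresponding condition simply as an earlier wound complication. The authors use the terms interchangeably.

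**5. Which visit?** The follow-up question in item 2 covers everything after the operation. That is a cumulative count, and it is complete at the last visit, 6 weeks.

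**The case for a change.** The strongest case for a change is that a primary endpoint and its time point belong in the protocol itself, and that the inconsistency sits in this document's own sentence. The follow-up question points to a cumulative count without fixing one. The outcome is worded in other ways too: item 1 expects fewer separated, broken-down or necrotic wounds, while item 2 asks about any postoperative complication. Naming one endpoint would take two sentences and add no procedure.

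Much of that stands as a remark on drafting. It is true that no endpoint or deciding visit is named in the text at hand, and a tidier sentence would cost little. It does not show that following the plan leads to a wrong result.

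The false-positive argument is sound in principle, but its size cannot be taken from the documents. A simulated free choice between breakdown and any complication at 6 weeks gives about 8% to 9.5% by z-test and 5% to 6% by Fisher's test. Allowing the 2-week visit as well gives about 12% to 15% and 8% to 9%. Those figures rest on assumed event rates, overlap and timing, none of which the Protocol supplies.

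Whether 20% is a well-supported control rate is a separate question. The Protocol applies it to high-risk women only, and says that infection risk in obese women doubles with each 5 BMI units above 30. A rate above the all-cesarean range is compatible with that.

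**Conclusion.** No change follows. The two terms are most plausibly loose synonyms for one event, and on that reading the calculation is sound: about 80 per arm for 20% against 5%, with 90% power (Fisher 88%) at the planned 100 per arm, assuming a two-sided 5% test. The powers of 30% to 81% drawn from the background rates belong to a different question and do not follow from the wording.

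The remaining gap is an unwritten definition of endpoint and time point. The natural reading, any wound complication from surgery through 6 weeks, agrees with the aim, the hypothesis, the benefit statement and the follow-up question. This rests on the text at hand; the separate research protocol and data collection form may already contain the definition.

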The PI and co-investigators will already be known to the patient per their clinical care and other non-clinical study staff will introduce themselves appropriately when presenting the research material. Please note: A Banner Employee will approach the subject first to ask them if they wish to learn more about the study, before any recruitment may take place. The consent document (see attached to this submission) will be used as an aid in discussing this research with patients. Though there is not script that the study personnel will read out to the patient, the sections of the consent form will be discussed with this patient before study proceedings are undertaken.

Additionally, patients who undergo a C-section when no study personnel are in the hospital may enroll via phone. Eligible patients who have been identified by a physician on Labor and Delivery will be asked if they would like to hear about the study. Those interested will discuss the study via phone with a member of the study staff on the VOTF using the phone disclosure as a guide. Patients will then be consented to the study in person, including access to PHI, by a member of the study staff before they leave the hospital.

We are requesting a partial PHI for recruitment purposes.

FORM: Application for Human Research		
NUMBER	FORM DATE	PAGE
F200	02/2014	9 of 14

7) Procedures involved in the Human Research

The randomization key will be provided by the department of statistics at the University of Arizona. Envelopes with a 1:1 study allocation (wound vac : no wound vac) will be provided and placed in the Pyxis on labor and delivery. The Pyxis is utilized for two reasons: 1) It is a standard place that the allocations can always be kept and 2) Nursing staff are required to access the Pyxis and an electronic log is kept of when the drawer was opened to retrieve an envelope with study allocation. This will provide adequate concealment of the allocations.

Once consent has been obtained from patients, an envelope containing the study allocation will be retrieved from the Pyxis.

- Non-wound vac patients will undergo wound closure with subcutaneous fat closure with Vicryl in all cases that this is practicable (in extremely thin patients, this may not be possible), followed by subcuticular skin closure also using Vicryl. A compression dressing will then be applied. This dressing is usually removed by the clinician the following day.

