- Wound vac patients will undergo wound closure with subcutaneous fat closure with Vicryl in all cases that this is practicable (in extremely thin patients, this may not be possible), followed by subcuticular skin closure also using Vicryl. The wound vac system will then be applied over the closed incision. This vac dressing will then be removed on the day of hospital discharge and replaced with a second bandage and the wound vacuum will be re-activated. The patient will remove both and discard on POD#7. This is per the manufacturer’s guidelines for length of use.
- If the patient fails the wound vac therapy- ie the wound separates and requires traditional wound care (packing, wet to dry dressing, etc), then the PICO system is no longer used as part of their care.

Essentially, the standard of care is to close the cesarean section incision. Different providers use different kinds of sutures (made of different material, and of different sizes) or staples to close the subcutaneous fat and the skin. Essentially what we are saying is that all patients in this study would have the subcutaneous fat and skin closed in the same manner (with Vicryl suture). To participate in the trial patients would have to agree to these closure materials - some patients would opt out of the study if they particularly wanted to have their skin closed with staples, for example (though I think that this would be rare as patients tend to prefer suture - it dissolves and does not have to be removed). We chose a standard closure with suture as there is evidence suggesting a lower rate of wound complications with suture as compared to staples.

We thought it would be unrealistic to try to standardize the entire operative approach (closure of the uterus, closure of the fascia) as the different providers working at the hospital may choose not to participate if the approach specified deviated too much from their usual technique.

FORM: Application for Human Research

NUMBER	FORM DATE	PAGE
F200	02/2014	10 of 14

8) Risks to subjects

The risks to subjects are minimal. All wounds will be closed in a way considered evidence-based. The only difference is the wound dressing applied over the closed wound and the time of removal. Though it is possible that the vac remaining over the wound may delay diagnosis of a wound complication this is very unlikely as the dressing is small, and a wound complication without significant surrounding erythema is uncommon.

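### The measures described for the Pyxis envelopes restrict and trace access, but do not support the protocol's claim that allocation is adequately concealed

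*Protocol*

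**What the plan says.** Section 3, item 7 of the protocol describes allocation in a few sentences.

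- Source: "The randomization key will be provided by the department of statistics at the University of Arizona".
- Vehicle, stored on the delivery unit: "Envelopes with a 1:1 study allocation (wound vac : no wound vac) will be provided and placed in the Pyxis".
- First reason for the Pyxis: "It is a standard place that the allocations can always be kept".
- Second reason, its access part: "Nursing staff are required to access the Pyxis".
- Second reason, its record-keeping part: "an electronic log is kept of when the drawer was opened to retrieve an envelope with study allocation".
- Conclusion: "This will provide adequate concealment of the allocations".
- Timing: "Once consent has been obtained from patients, an envelope containing the study allocation will be retrieved from the Pyxis".

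The text does not describe the envelopes as sealed, opaque or numbered. It does not require use in order, marking with a patient identifier before opening, or a check of the log against enrolment.

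On timing, Section 3, item 10 names the pre-operative area, a clinic room or a laboring room as places for consent. On closure, item 7 gives both arms the same instruction. For the device arm it reads "Wound vac patients will undergo wound closure with subcutaneous fat closure with Vicryl in all cases that this is practicable", and very thin patients are the example of an exception. Subcuticular Vicryl to the skin follows in both arms, and then the compression dressing or the device.

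**The concern.** Allocation is concealed when the person deciding whether and when to enrol a patient can neither know nor choose the next assignment. The protocol asserts this property and gives its grounds, but the grounds concern where the envelopes are kept, who can reach them and when the drawer was opened. A drawer can be locked and logged while someone with access still looks ahead, or takes an envelope other than the next one.

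This protection is needed because investigators identify patients in the course of their own clinical work (item 6), and the eligible conditions in that item form a mixed group that may differ in wound risk. If lower-risk women went preferentially to the device, the device would look better than it is, and nothing in the outcome data would show it.

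A separate issue is timing. If the envelope is retrieved when consent is given in clinic or in a laboring room, the operating team may know the arm before closing the wound. That concerns performance bias, not concealment, but one change to the procedure can deal with both.

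**Working it through.** **Step 1. Each stated measure against what concealment requires.**

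| Measure in item 7 | What it does | Hides the next assignment? | Enforces order of use? |
|---|---|---|---|
| Fixed storage place | Envelopes can be found | No | No |
| Access through nursing staff | Restricts who opens the drawer | Not from those staff | No |
| Log of drawer openings | Traces access afterwards | No | Not as described |
| Key from statistics department | Keeps generation of the sequence off the unit | Not once envelopes are on the unit | No |
| Retrieval after consent | Keeps the arm from influencing that patient's consent, if nobody has looked ahead | No | No |

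No row has a yes in either of the last two columns, so the asserted property does not follow from the procedure as written. The last two measures do lower the risk.

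**Step 2. Timing.** Item 7 makes consent the condition for retrieval and sets no later limit. Item 10 allows consent in rooms used before surgery. Together they permit, but do not require, opening before the operation. What a surgeon could then vary is limited: fat and skin closure are specified identically in both arms, with one exception on practicability. Item 7 deliberately leaves uterine and fascial closure unstandardised.

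**Step 3. Illustration of size.** The protocol has no figure to reproduce here. From item 5 come 100 patients per arm and a 20% complication rate. Everything else is assumed: no true effect, half the patients at high risk *h* and half at low risk *l* with mean 0.20, and a fraction *f* of assignments steered, always with low-risk women to the device and high-risk women to control.

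- Device arm rate = (1 − f) × 0.20 + f × l
- Control arm rate = (1 − f) × 0.20 + f × h
- Spurious difference = f × (h − l)
- Standard error ≈ √(2 × 0.20 × 0.80 / 100) = 0.0566
- Chance of a false positive favouring the device ≈ Φ(difference / 0.0566 − 1.96)

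| Assumed split h/l | f | Device | Control | Difference | False positive, one-sided |
|---|---|---|---|---|---|
| any | 0 | 20.0% | 20.0% | 0 | 2.5% |
| 25%/15% | 0.10 | 19.5% | 20.5% | 1.0 point | 3.7% |
| 30%/10% | 0.10 | 19.0% | 21.0% | 2.0 points | 5.4% |
| 30%/10% | 0.20 | 18.0% | 22.0% | 4.0 points | 10.5% |

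For the 30%/10% split, a simulation of 40,000 null trials of 200 patients gave 2.4%, 5.4% and 10.5% at f = 0, 0.10 and 0.20, in agreement.

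**The case against.** The strongest defence is that the protocol relies on more than a log. Nursing access is a real control, the key is prepared outside the clinical team, and no envelope is drawn before consent. The document is also an ethics application, and its Section 4 lists a separate research protocol that is not at hand and may specify the envelopes. All of this stands. It means that silence about seals and numbering cannot itself be counted as the error. What can be faulted is that item 7 declares concealment adequate and gives its grounds, and those grounds do not carry the claim.

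A reader might infer more than the text supports:

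- **That the envelopes are unsealed, or that allocations were steered.** Neither is shown.
- **That the log cannot tell which envelope was taken or for whom.** The protocol states one thing the log records and does not list what it omits.
- **That a surgeon's knowledge of the arm is a failure of concealment.** It arises after assignment. Better envelopes alone would not remove it, and the identical closure instruction narrows it.
- **That concealment guards against biased wound assessment by investigators who know the arm.** That is detection bias, which concealment does not address.
- **That the figures above size this trial's bias.** They return the assumptions put in. Halving the assumed risk gap halves the difference, and the model sorts every steered patient perfectly and always in the device's favour.

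**Conclusion.** The point holds in a limited form. On the measures described, access to the envelopes is restricted and traceable, but learning or choosing the next assignment is not prevented, so the word *adequate* is not justified. This is a statement the protocol makes on insufficient grounds, and not a detail left to an analysis plan.

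Possible knowledge of the arm before surgery is a secondary and smaller matter of performance bias.

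No size can be attached to this trial. At 10% steering, the illustration runs from 1.0 point with about 3.7% false positives (25%/15% split) to 2.0 points with 5.4% (30%/10% split), against a nominal 2.5%. The steering fraction and the risk split are both assumptions; only the 20% mean rate and 100 per arm come from the protocol. The change is worth making because it is cheap and the bias, if it occurred, could not be repaired in the analysis.

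**What to change.** Replace the concealment sentence in Section 3, item 7 with a procedure that achieves it:

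1. Sequentially numbered, opaque, sealed envelopes, prepared off the unit and used in strict order.
2. Study ID, date and time written on the envelope before it is opened.
3. Opening only after skin closure is complete, just before the dressing is applied. This is feasible because closure is the same in both arms and the device goes over the closed incision. It also removes the possibility that the arm is known during closure.
4. Reconciliation of envelope numbers with the Pyxis log and the enrolment list at set intervals.

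The Pyxis and its log can stay as secure storage and an audit trail, without the claim that they conceal.

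Cost: revised wording, envelope printing and brief reconciliation by existing staff. The practical downside is that the envelope and the device must be at hand in theatre at closure.
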